Appendix Table 1. Hidradenitis Suppurativa Physician's Global Assessment Scale

Rating	Description
Clear	0 abscesses, 0 draining fistulas, 0 inflammatory nodules, and 0 noninflammatory nodules
Minimal	0 abscesses, 0 draining fistulas, 0 inflammatory nodules, and presence of noninflammatory nodules
Mild	0 abscesses, 0 draining fistulas, and 1–4 inflammatory nodules or 1 abscess or draining fistula and 0 inflammatory nodules
Moderate	0 abscesses, 0 draining fistulas, and ≥ 5 inflammatory nodules or 1 abscess or draining fistula and ≥ 1 inflammatory nodule or 2–5 abscesses or draining fistulas and < 10 inflammatory nodules
Severe	2–5 abscesses or draining fistulas and ≥ 10 inflammatory nodules
Very severe	> 5 abscesses or draining fistulas

Table 1: Schedule of Events

	Baseline Visit Day 0	Phone call 1 Day 7	Follow-Up Visit Day 14	Phone call 2 Day 21	Phone call 3 Day 28	Phone call 4 Day 35	End of Treatment Visit Up to Day 42 after Baseline Visit
Visit Window		7 +/- 3 Days from Baseline Visit	14 +/- 3 Days from Baseline Visit	7 +/- 3 Days from Follow-Up Visit	14 +/- 3 Days from Follow-Up Visit	21 +/- 3 Days from Follow-Up Visit	28 +/- 3 Days from Follow-Up Visit
Visit #	0		1				2
Informed Consent/PHI authorization	X						
Demographics	X						
Medical History ^A	X						
Concomitant Medications & Procedures Assessment	X		X				X
Physical Exam ^B	X		X				X
Inclusion/Exclusion Determination	X						
Wound(s) Photograph	X		X				X
Dermatology Life Quality Index (DLQI)	X						X
Average 24 hours pain Score (NRS)	X	X	X	X	X	X	X
Maximal 24 hours pain Score (NRS)	X	X	X	X	X	X	X
Review Dressing Logs			X				X
Sleep assessment	X	X	X	X	X	X	X
Drainage assessment	X	X	X	X	X	X	X

Dressing Satisfaction	X		X				X
Dressings' Ease of Use	X		X				X
Odor assessment	X	X	X	X	X	X	X
HS-PGA	X		X				X
Wound Swab Sample Collection	X		X				X
Adverse Events Assessment			X				X

A: Detailed HS history will be gathered, including current wound care regime (types and number of dressings utilized per week, including an estimate of anticipated dressings needed per week), exacerbating and alleviating factors; B: Hurley staging will be assessed, as well as types (inflammatory, sinus tracts, ulcerations), number, and location of lesions

5) Data and Specimen Banking*

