Wound Dressing in Patients with Hidradenitis Suppurativa: A Pilot Study

STUDY PROTOCOL
PROTOCOL NUMBER 20191046
NCT04194541

Principal Investigator:
[name]

[name] Department of Dermatology & Cutaneous Surgery, University of Miami Miller School of Medicine.

[contact] or [contact] (24-hour page operator)

Email Address: [contact]

Protocol Version No.3 Date: April 6, 2022

1) Objectives*

The primary purpose of this research is to determine how the types of wound dressings affect quality of life for people with Hidradenitis Suppurativa (HS). The secondary purpose is to evaluate the utility of a starter kit concept for wound care in people with HS.

1. Primary outcome: quality of life as measured by the DLQI instrument.
2. Secondary outcomes include:
 - a. Average pain as measured on NRS
 - b. Maximal pain as measured on NRS
 - c. Sleep assessment as measured on 5-point likert scale
 - d. Drainage assessment as measured on 4-point likert scale
 - e. Odor assessment as measured on 4-point likert scale
 - f. Patients' overall preference of dressings for HS as measured on a 5-point likert scale
 - g. Which dressings work best for which parts of the body as measured by patient log
 - h. Frequency of dressing changes required as measured by patient log
 - i. *HS-Physician's Global Assessment (HS-PGA)*
 - j.

Study Endpoints:

Primary endpoint	Change in DLQI from baseline to week 6
Secondary endpoint	Change in average pain NRS from baseline to week 6
Secondary endpoint	Change in maximal pain NRS from baseline to week 6
Secondary endpoint	Change in sleep rating from baseline to week 6
Secondary endpoint	Change in drainage rating from baseline to week 6
Secondary endpoint	Change in odor rating from baseline to week 6

Secondary endpoint	Overall dressing preference for HS as noted by subjects on patient log
Secondary endpoint	Dressing preference for body parts as noted by subjects on patient log
Secondary endpoint	Average frequency of dressing changes as noted by subjects on patient log
Secondary endpoint	Change in HS-PGA at 6 weeks after initial assessment

2) Background*

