We will additionally study how the usage of antimicrobial dressings will have an effect on the wound microbiome in order to see how this affects healing in the setting of HS. The presence of bacteria in the wound bed will be determined by analyzing the collected wound swab samples. Standard molecular techniques will be utilized for bacterial analysis. The purpose of collecting swab samples is purely qualitative in its intent to gather data on bio-bioburden and microbiome composition. Ulcer swab results are not indicated for therapeutic treatment nor diagnosis of infection. The results of sample swabs will not have an impact on the treatment plan for each participant.

3) Inclusion and Exclusion Criteria*

Inclusion criteria:

- Men and women ≥ 18 years of age
- Diagnosed with Hidradenitis Suppurativa (all stages of disease) by Dermatologist
- Presence of at least one lesion with active drainage
- Willing and able to provide informed consent

Exclusion criteria:

- Subjects younger than 18-years-old.
- Prisoners
- Pregnant or lactating women
- Adults unable to consent

4) Procedures Involved*

Study duration:

Each subject will have three visits total over a 6-week period.

Recruitment and procedures:

Participants recruited for this study will be patients at University of Miami Hospital (UMH) outpatient dermatology clinics and wound care centers, who present to UMH with a diagnosis of Hidradenitis Suppurativa (HS). During their office visit, patients will be invited to participate in a six-week study to determine which dressings are best suited for patients with HS.

Potential subjects will be informed of the study during their standard of care appointment and then asked if they would like to participate. After signing informed consent, a physical exam will be performed and information on the subjects' demographics, and medical history will be collected (visit 0). Quality of life will be assessed with DLQI instrument. Maximal and average pain will be assessed on a 5-

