point likert scale. Quality of sleep, drainage, and odor will be assessed as well (Table 1). Photographs and measurements will be taken of wounds associated with HS. Any active wounds will receive standard of care, including cleaning and debridement to remove all nonviable soft tissue from the wound by scalpel, tissue nippers and/or curettes when appropriate. Wound swab samples will be collected from patients from one active wound at each visit. This site will be identified during the baseline visit. If debridement is indicated as part of standard care, prior to debridement of the wound, a wound swab sample will be collected from the wound bed. In circumstances where a layer of nonviable tissue is preventing swab collection, the swab sample should be collected during the course of the debridement process wherein the wound bed has been exposed. Subjects will be provided with a kit that will include 3 types of FDA-cleared dressings (1) Cutimed® Sorbact® Hydroactive B, 2) Cutimed® Siltec®, and, 3) Sorbion® Sana multi-star) that are available on the market and general wound care supplies (i.e. tape, gauze) that are also FDA-cleared and available on the market. Dressing instructions involve applying desired dressing daily to affected areas and securing with tape as needed. Participants may change dressings as needed. Instructions will be reviewed with participants upon enrollment. Participating subjects will also be given a 2-week log where they will be instructed to fill in which dressings they used on which wounds, and how often they changed the dressings.

Subjects will receive weekly phone calls in between follow ups (for a total of 4 phone calls) by the research team where they will be asked to answer questions on average and maximal pain, quality of sleep, drainage and odor. Subjects will be asked to follow up in 14 +/- 3 days from visit 0 (visit 1), at which point the physical exam will be performed. Maximal and average pain will again be assessed on a 5-point likert scale. Quality of sleep, drainage, and odor will be assessed as well (Table 1). Photographs and measurements of HS wounds will be taken and the dressing logs will be collected and evaluated. Wound swab samples will be collected from the wound that was pre-identified at baseline visit. Participants will share with study personnel which dressings were most useful to them, and this will dictate the dressing type that each subject receives for the remaining 4 weeks of the study period.

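### One self-selecting group and one DLQI score per subject cannot show how dressing types affect quality of life; DLQI is also omitted at Visit 1, where the regimen changes

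*Combined protocol and SAP*

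**What the plan says.** **Objective and endpoint.** Section 1) Objectives states: "The primary purpose of this research is to determine how the types of wound dressings affect quality of life". The Study Endpoints table makes this "Change in DLQI from baseline to week 6". Secondary outcome g is "Which dressings work best for which parts of the body as measured by patient log". Section 4) Procedures Involved presents the trial to patients as "a six-week study to determine which dressings are best suited for patients with HS".

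**Regimen.** Under section 4 every subject receives the same kit with three dressing types. Choice is left to the subject: "Dressing instructions involve applying desired dressing daily to affected areas". In the log they "fill in which dressings they used on which wounds, and how often they changed the dressings". At Visit 1 (day 14 +/- 3) they say which dressings were most useful, and "this will dictate the dressing type that each subject receives for the remaining 4 weeks of the study period". No randomisation, assigned sequence or control group is described.

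**Schedule.** Table 1 marks the "Dermatology Life Quality Index (DLQI" row at baseline and end of treatment only. Pain, sleep, drainage, odor, satisfaction, ease of use and HS-PGA are all also taken at Visit 1.

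**Numbers and analysis.** Section 14) Local Number of Subjects expects high drop-out and enrols 30 to reach 20, with no rate or timing. Section 6) Data Management plans mean and range for continuous variables and chi-squared or Fisher tests for categorical ones. It gives no missing-data rule and no analysis of DLQI by dressing type.

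**The concern.** There are two separate problems.

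**(B) The objective, the main point.** The primary question is about types of dressing, but the primary endpoint contains no contrast between types. A before-after DLQI change could be reported as an effect of dressing type when neither the design nor a per-subject score can show one.

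**(A) The schedule, a lesser point.** DLQI is the only patient-reported rating in Table 1 that is skipped at Visit 1, which is where the regimen changes. No quality-of-life value describes the kit phase. Subjects lost between Visit 1 and Visit 2 contribute nothing on the primary outcome after baseline, so DLQI cannot show whether they were already doing differently from those who stayed.

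**Working it through.** **Part B: objective set against design.** No arithmetic applies.

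1. An effect of type needs outcomes under different types in comparable subjects or periods. Here there is one group, and type is self-chosen in both phases. Any DLQI difference by type is confounded with the reasons for choosing it.
2. Note A to Table 1 records the wound care regime in use at entry, so baseline serves only as a before-after reference. Standard-of-care debridement, concomitant treatment, the natural course of the disease and regression to the mean (entry requires active drainage) can all move DLQI.
3. Dressings are logged per wound, and outcome g expects different types on different body parts. DLQI is one score per subject and visit. A subject using two or three types at once has no DLQI that belongs to one of them.

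**Part A: counts.** Enrolling 30 to reach 20 implies a loss of (30 − 20)/30 = 33.3%. This is back-calculated; the protocol states no rate.

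Subjects with any post-baseline DLQI, if Visit 1 is added = completers + losses × share lost after Visit 1.

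| Completers of 30 | Share of losses after Visit 1 | As planned | With Visit 1 DLQI |
|---|---|---|---|
| 20 | all | 20 | 20 + 10 = 30 |
| 20 | half | 20 | 20 + 5 = 25 |
| 20 | none | 20 | 20 |
| 15 (assumed) | half | 15 | 15 + 7.5 = 22.5 |
| 25 (assumed) | half | 25 | 25 + 2.5 = 27.5 |

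Under an assumed constant drop-out hazard, 30 × (2/3)^(14/42) = 26.2 subjects reach Visit 1, so about 6 of the 10 losses come later.

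**Part A: precision of a phase change.** The documents give no DLQI SD or correlation, so both are assumed. SD of change = SD × √(2(1 − r)); 95% half-width = t(0.975, n − 1) × SD of change / √n. With SD 7, the SD of change is 7.0 at r = 0.5 and 5.4 at r = 0.7.

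| n | r = 0.5 | r = 0.7 |
|---|---|---|
| 20 | 3.3 | 2.5 |
| 25 | 2.9 | 2.2 |
| 30 | 2.6 | 2.0 |

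Over SD 5 to 9 and n = 20 to 30 the half-width runs from 1.4 to 4.2 points.

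**Part A: completers against later drop-outs on Visit 1 change.** Half-width = t(0.975, a + b − 2) × SD of change × √(1/a + 1/b). At SD 7 this is 4.3 to 5.6 points for 20 v 10 and 5.6 to 7.2 for 20 v 5 (3.1 to 9.3 over SD 5 to 9). Only a large difference would show.

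**Part A: simulation of drop-out bias.** Assumptions: 4,000 runs per scenario, n = 30, SD 7, means 0, −1.5 and −3.0 at the three visits. Correlations (baseline–Visit 1 / Visit 1–week 6 / baseline–week 6) are 0.5/0.5/0.5, 0.6/0.6/0.5, 0.7/0.7/0.5 and 0.7/0.7/0.7. One-third are lost. Early losses are random; late losses are logistic with slope 1 or 2 per SD, with less improvement giving more drop-out. The true week-6 change is −3.0.

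| Late drop-out follows | Late share | Completers' mean | Repeated-measures model |
|---|---|---|---|
| Visit 1 change | all | −3.8 to −4.8 | within 0.1 of −3.0 |
| Visit 1 change | half | −3.5 to −4.2 | within 0.1 of −3.0 |
| Unseen later change | all | −3.8 to −4.9 | −4.1 to −5.2 |
| Unseen later change | half | −3.5 to −4.2 | −3.7 to −4.3 |

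In the last two rows the model is worse than completers alone, though only marginally at correlations 0.7/0.7/0.5. With random drop-out neither is biased and the model lowers the standard error little: with all losses late, by 1.24 − 1.18 = 0.06 to 1.59 − 1.47 = 0.12. On Visit 1 change, later drop-outs minus completers is +4.5 to +9.2 if drop-out follows Visit 1 change, but −0.8 to −4.6 if it follows later change. The check can therefore point the wrong way.

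**The case against.** **The schedule matches the endpoint.** DLQI is marked at exactly the two visits that the endpoint needs, and kit followed by preferred dressing can be read as one six-week strategy. This stands: no passage requires a phase-specific DLQI, so Part A is an improvement and not the correction of an error.

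**Other data cover the gap.** Symptoms are collected at every visit and call, and satisfaction, ease of use and HS-PGA at Visit 1. Drop-outs can be compared with completers on these and on baseline DLQI, which every subject has. This also stands. What is missing is narrower: a change in the primary outcome during the kit phase.

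**The numbers are modest.** Precision barely improves, the completer check is coarse, and the model helps under only one kind of drop-out. This is true, and it is why the case for a Visit 1 DLQI rests on the phase split and on data from later drop-outs.

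**The dressing type is singular after Visit 1.** Some subjects may use one supplied type for the last 4 weeks, so some week-6 scores may follow use of a single type. This is granted. Their change still starts from baseline and spans the kit phase, and confounding by choice remains.

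**This is a pilot, and no comparison by type is planned.** That excuses small numbers and the lack of a control. It does not excuse a primary objective that the design cannot answer.

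**Conclusion.** Both parts hold. Part B follows from the protocol's text alone: the primary endpoint cannot answer the stated primary objective at any sample size. It should be changed because it governs what the trial may conclude.

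Part A is a cheap improvement. If 20 of 30 complete, a Visit 1 DLQI raises the number with any post-baseline value from 20 to between 20 and 30. It also allows a kit-phase change to be described to within about 2.0 to 3.3 points at an assumed SD of 7 (n = 20 to 30). The drop-out timing, SDs, correlations and drop-out mechanisms are assumptions, and the size and direction of any real drop-out bias cannot be known from the documents.

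**What to change.** **Objective (B).** Reword the primary objective to: describe change in DLQI from baseline while using the kit and then the preferred dressing. Treat any DLQI breakdown by chosen dressing as descriptive. Leave questions about dressing type to the preference, body-site, satisfaction, ease-of-use and log outcomes already planned. The cost is a wording change and a more modest aim.

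**Schedule and analysis (A).**

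1. Mark DLQI at Visit 1 in Table 1, name it in the Visit 1 text, and ask it at last contact with subjects who withdraw; the weekly calls offer a route.
2. Report the baseline-to-Visit 1 and Visit 1-to-week 6 changes as uncontrolled descriptive figures, stating that phase is confounded with time.
3. Keep the observed week-6 change, with its number of subjects, as the main result. Compare Visit 1 change between completers and later drop-outs, stating that this is coarse and cannot detect drop-out driven by later change.
4. Show any repeated-measures estimate as a sensitivity analysis only, stating that it removes bias only if drop-out depends on observed values.

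The cost is one questionnaire of a few minutes at an existing visit, a question at last contact, and a short amendment. Limits remain: the week-6 endpoint is still observed only in completers, and subjects lost before Visit 1 are not helped unless they are reached.

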6.1 Collection and Analysis of Wound Swabs

The following study procedures for wound swabs will be performed at the pre-designated wound sites only. Wound swab samples will be collected at the Baseline Visit 0, Follow-Up Visit 1, and Follow-Up Visit 2.

Wound swabs will be collected from all study wounds. If debridement is indicated as part of standard care, wound swabs will be performed prior to the debridement. Wound swab sample will be collected from the wound bed using the Levine technique. In circumstances where a layer of nonviable tissue is preventing swab collection, the swab sample should be collected during the course of the debridement process wherein the wound bed has been exposed. Wound swab samples from enrolled subjects will be collected and sent out for further processing and analysis to [name] laboratory. The labels of the tubes will be coded to protect the identity of the subjects. Samples will be stored in a -80°C freezer prior to shipment to the processing laboratory. Samples will be shipped on dry ice.

6.2 Dressing Logs and Photographs

The dressing logs and photographs collected from each patient will be de-identified and stored in a computer located in the Dermatology Research office. The computer

is located in a locked room in the University of Miami Hospital West Building, Room 506, [name].

Statistical analysis will be performed using software already available in the lab. This information will be protected in a locked office (see Confidentiality section below) and will only be able to be accessed by the primary investigator and the co-investigators. The photographs will then be downloaded as encrypted, de-identified JPEG/TIFF files and stored in the PI computers protected by login and password (see section 16).

6) **Data Management***

The investigator (or research staff) will record the data collected in a manner that does not include any direct identifiers of the subject. The investigator will assign a code to each subject and link the code to the subject's identity. The link to the subject's identity will be maintained on a document separate from the research data. Both documents will be stored on password-protected media on a University of Miami encrypted device. The data will be stored for at least 3 years after the study has concluded and will be destroyed at the earliest opportunity in accordance with University of Miami's policies thereafter. Data will only be accessed by designated study team members.

Statistical analysis of collected data will be performed using IBM SPSS Statistics for Windows (IBM Corporation, Armonk, NY, USA). Mean and range will be calculated for continuous variables. Pearson's chi-squared test will be used to test for independence between categorical variables; for expected values less than 5, Fisher's exact test of independence will be used.

Adverse Events

7) **Adverse Events***

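### The plan gives no SD, confidence interval or paired method for its change-from-baseline endpoints, so the primary report may not show whether the DLQI change is distinguishable from zero

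*Combined protocol and SAP*

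**What the plan says.** Section 1 (Objectives, Study Endpoints) gives the primary endpoint as "Change in DLQI from baseline to week 6". It lists nine secondary endpoints. Six are changes: average pain, maximal pain, sleep, drainage ("Change in drainage rating from baseline to week 6"), odor and HS-PGA ("Change in HS-PGA at 6 weeks after initial assessment"). The HS-PGA wording differs from the others, but Table 1 schedules it at the baseline visit, so it is a change from baseline too. The other three come from the patient log: overall preference, preference by body part, and frequency of dressing changes.

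The named statistical methods are all in section 6 (Data Management). For continuous data: "Mean and range will be calculated for continuous variables". For categorical data, Pearson's "chi-squared test will be used to test for independence between categorical variables", with Fisher's exact test when expected counts are below 5. No section names an SD, a standard error, a confidence interval or a paired method.

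Table 1 schedules DLQI only at baseline and end of treatment. Section 14 aims to reach 20 subjects and enrols 30 because many are expected to drop out. Section 4 treats an HS-PGA fall of 2 points or more as a meaningful response, with no planned summary of that proportion.

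**The concern.** This is a single group measured before and after, so what matters is the within-subject change and how precisely it is estimated. A mean and a range give the size of the change and its two most extreme values. They do not give the spread of the other subjects, which is what determines the interval. Two quite different results could be reported identically.

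For the ordinal ratings there is a mismatch of method. A test of independence asks whether two categorical variables are associated. Cross-tabulate baseline against week-6 drainage. If every subject keeps the same rating the association is perfect, and if every subject improves by exactly one category it is equally perfect. The test cannot tell these cases apart, so it does not measure change.

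At stake is whether a reader of the primary result can judge if the observed DLQI change could be chance variation, and whether four of the secondary change endpoints have any suitable summary.

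**Working it through.** **Inputs from the protocol.** Target n = 20 and enrolled n = 30 (section 14); one primary and nine secondary endpoints (section 1). No SD, effect size, power or dropout rate is given, so there is no precision figure to reproduce. The step from 20 to 30 implies 1 − 20/30 = 33.3% dropout, but that is back-calculated from the two numbers and checks nothing.

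**Endpoint count.** Average pain, maximal pain, sleep, drainage, odor and HS-PGA are six changes. With three log-based endpoints, 6 + 3 = 9.

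**Precision that the plan omits.** The 95% half-width for a mean paired change is t(0.975, n−1) × SD of change / √n. In units of the SD of change:
- n = 15 (assumed, if the target is missed): 0.554
- n = 20: 0.468
- n = 30 (nobody drops out): 0.373

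For an assumed SD of change from 4 to 8 DLQI points, the half-width runs from 1.87 to 3.74 points at n = 20, and from 1.49 to 2.99 at n = 30.

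**What the range can and cannot say.** Take n = 20, range of width R, mean at mid-range.
- Smallest SD (one subject at each extreme, the rest at the mean): R/√(2(n−1)) = R/√38 = 0.162R
- Largest SD (half the subjects at each extreme): (R/2)√(n/(n−1)) = 0.5R × √(20/19) = 0.513R
- Half-widths: 0.468 × 0.162R = 0.076R, and 0.468 × 0.513R = 0.240R
- Ratio: √(n/2) = √10 = 3.16

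So a mean change beyond 0.240R excludes zero whatever the SD, and one below 0.076R cannot exclude it. In between, the report does not settle the matter. For an illustrative R = 20 points, the unsettled zone is a mean change between about 1.5 and 4.8 points.

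**Two illustrative data sets** (invented change scores, n = 20, both with mean −2 and range −12 to +8):
- Set A: −12, 8, −5 (×2), −4 (×3), −3 (×3), −2 (×2), −1 (×3), 0 (×3), 1 (×2). Sum of squared deviations 266; SD = √(266/19) = 3.74; half-width 0.468 × 3.74 = 1.75; interval −3.75 to −0.25.
- Set B: every integer from −12 to 8 except −2. Sum of squared deviations 770; SD = √(770/19) = 6.37; half-width 2.98; interval −4.98 to +0.98.

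The planned summary of the change is the same for both, yet one interval excludes zero and the other does not.

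**HS-PGA response.** For an illustrative 6 of 20 responders (30%), the exact 95% interval is 11.9% to 54.3%. A bare percentage would hide that width.

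**The case against.** The strongest reply has four parts.

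*The range does carry information.* This stands. By the bound above, a mean DLQI change of −5 with range −15 to +5 would exclude zero with no SD reported, since the half-width cannot exceed 4.8. It would be wrong to say that the planned report could never show a change distinguishable from zero. It may not show it.

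*Nothing is lost.* This also stands. Both DLQI assessments are collected, section 6 keeps the data for at least 3 years, and the paragraph does not forbid further summaries. The gap is in what the plan commits to report.

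*A pilot needs no hypothesis test.* Agreed, and none is required here. An interval is not a test, and the stated primary purpose, learning how dressings affect quality of life, is poorly served by an estimate without one. Tests on scales of four to six levels with about 20 subjects would also meet many ties, which is a reason to keep them optional.

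*Chi-squared and Fisher tests have a legitimate place.* They do, for comparisons between different subjects. At visit 1 each subject's preference is recorded and "this will dictate the dressing type that each subject receives for the remaining 4 weeks of the study period"; relating the dressing kept to a categorical outcome would be such a use. It does not supply a method for paired change.

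A reader might also infer two further harms. One is that week-6 and baseline means would be taken on different subjects, so that dropout distorts the change. The plan does not say how the mean is formed, but the endpoint is worded as a change, which reads naturally as within-subject, and nothing gives a baseline difference between dropouts and completers. The other is that the study would fail to size a later trial. Beyond the word pilot, the protocol states no such purpose.

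**Conclusion.** The point holds as a shortfall in planned reporting that should be fixed. Following section 6 as written, the primary DLQI change would be reported without a usable measure of precision, and sleep, drainage, odor and HS-PGA change would have no suitable method. At n = 20 the range leaves the half-width uncertain by a factor of 3.2 (0.076R to 0.240R).

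The factor rests on n = 20, a mean at mid-range and a t-based interval. The example change scores, the SDs of 4 to 8, the R of 20 and the 6 of 20 responders are illustrations, because the protocol gives no such figures.

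Two nearby contradictions are separate matters and add no weight here. Section 1 has "Average pain as measured on NRS" while section 4 has "Maximal and average pain will again be assessed on a 5-point likert scale". Section 4 also describes HS-PGA as summed points, while the scale table gives six categories. Both pairs must be reconciled.

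**What to change.** In section 6 (Data Management), replace the mean-and-range sentence, for the change endpoints, with the following:

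- **DLQI (primary):** mean within-subject change from baseline to week 6 with SD, range and paired 95% confidence interval, in subjects with both assessments. Give the number analysed, the number missing week 6, and baseline DLQI in each of those groups. A subject who leaves before the final visit has no DLQI change, so these counts matter.
- **Average and maximal pain:** the same summary of change, on whichever scale the reconciled text specifies.
- **Sleep, drainage, odor and HS-PGA:** the distribution of within-subject change. If any test is made, use a paired one, for example Wilcoxon signed-rank.
- **HS-PGA 2-point reduction:** the proportion with an exact 95% interval, once the scoring descriptions agree.
- **Chi-squared and Fisher tests:** keep for comparisons between different subjects.
- **Interpretation:** state that intervals are descriptive and that change in a single uncontrolled group cannot be attributed to the dressings.

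The cost is a rewritten statistical paragraph and slightly more analysis. No new visits, subjects or data are needed, because every quantity comes from assessments already in Table 1. Reconciling the pain and HS-PGA wording is a separate edit, but it has to come before those two summaries are final.
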